9.1 Definitions

9.1.1 Adverse Event

An **adverse event** (AE) is any symptom, sign, illness or experience that develops or worsens in severity during the course of the study. Intercurrent illnesses or injuries should be regarded as adverse events. Abnormal results of diagnostic procedures are considered to be adverse events if the abnormality:

- results in study withdrawal
- is associated with a serious adverse event
- is associated with clinical signs or symptoms
- leads to additional treatment or to further diagnostic tests
- is considered by the investigator to be of clinical significance

For FDA regulated studies the FDA defines an adverse event as the following:

Adverse event means any untoward medical occurrence associated with the use if a drug in humans whether or not considered drug related.

9.1.2 Serious Adverse Event

Serious Adverse Event

Adverse events are classified as serious or non-serious. A **serious adverse event** is any AE that is:

- fatal
- life-threatening
- requires or prolongs hospital stay
- results in persistent or significant disability or incapacity
- a congenital anomaly or birth defect
- an important medical event

Important medical events are those that may not be immediately life threatening, but are clearly of major clinical significance. They may jeopardize the subject, and may require intervention to prevent one of the other serious outcomes noted above. For example, drug overdose or abuse, a seizure that did not result in in-patient hospitalization or intensive treatment of bronchospasm in an emergency department would typically be considered serious.

All adverse events that do not meet any of the criteria for serious should be regarded as **non-serious adverse events**.

9.2 Recording of Adverse Events

At each contact with the subject, the investigator will seek information on adverse events by specific questioning and, as appropriate, by examination. Information on all adverse events will be recorded immediately in the source document, and also in the appropriate adverse event module of the case report form (CRF). All clearly related signs, symptoms, and abnormal diagnostic procedures results should be recorded in the source document, though should be grouped under one diagnosis.

All adverse events occurring during the study period will be recorded. The clinical course of each event will be followed until resolution, stabilization, or until it has been determined that the study intervention or

CONFIDENTIAL

This material is the property of the University of Pennsylvania.

participation is not the cause. Serious adverse events that are still ongoing at the end of the study period will be followed up to determine the final outcome. Any serious adverse event that occurs after the study period and is considered to be possibly related to the study intervention or study participation will be recorded and reported immediately.

9.3 Relationship of AE to Study

The relationship of each adverse event to the study procedures should be characterized. The PI or medical monitor will determine how the relationship of the AE will be classified as:

- likely related – a well-known effect of the device or clearly not related to the subject or environmental factors
- probably related – is known or suspected effect of device or cannot be readily explained by subject or study procedures
- possibly related – is a possible effect of the device or can be explained by the subject or study procedures
- unlikely related – is not a suspected effect of the device or can readily be explained by the subject or environmental factors
- unrelated – is not a known effect of the device and can readily be readily and easily explained by the subject or environmental factors

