9.4.2 Investigator reporting: notifying the study sponsor

Investigators from all participating sites should report all unexpected and related adverse events, regardless of whether they are serious or not, and all unanticipated problems to the sponsor.

Any study-related unanticipated problem posing risk to subjects or others, and any type of serious adverse event, will be reported to the study sponsor by telephone within 24 hours of the event. To report such events, a Serious Adverse Event (SAE) form will be completed by the investigator and emailed to the study sponsor within 24 hours. The investigator will keep a copy of this SAE form on file at the study site. Report serious adverse events by sending via email to:

CONFIDENTIAL

This material is the property of the University of Pennsylvania.

[Galderma Laboratories, L.P., email: [name] <[contact]>]

Within the following 48 hours, the investigator will provide further information on the serious adverse event or the unanticipated problem in the form of a written narrative. This should include a copy of the completed Serious Adverse Event form, and any other diagnostic information that will assist the understanding of the event. Significant new information on ongoing serious adverse events should be provided promptly to the study sponsor.

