11.1 Risks

All treatments used in this protocol will be used according to the FDA approved intended use. No unexpected risks should occur. Risks that may be experienced from any injection are swelling bruising, redness, itching, infection, or pain.

All HA containing products have the risk of potential tissue loss if there is unrecognized intravascular injection of the fillers. All HA fillers are dissolvable and if you are strongly dissatisfied with the treatment filler or if there is evidence of tissue threat, HA can be removed with hyaluronidase (Vitrase)®. Restylane Silk carries an extra risk of hyperpigmentation to the risks from injection listed above. A risk related to all injectables used in this study is unevenness or lumps.

CONFIDENTIAL

This material is the property of the University of Pennsylvania.

Reproductive risks: If patient is of child-bearing potential, a urine pregnancy test may be administered prior to injection to confirm negative pregnancy status. The effects of this drug/device, there could be serious harm to unborn children or children who are breast-feeding. These effects could also harm the mother.

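### Section 9.3 grades adverse events for relation to the study procedures, yet two of its five grades list those procedures as an alternative cause, so an injection-caused event may be graded down and has no single grade

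*Combined protocol and SAP*

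**What the plan says.** Section 9.3 opens with the object of the assessment: "The relationship of each adverse event to the study procedures should be characterized". Section 6, headed as study procedures, includes the injections (6.1.2).

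Four of the five grades that follow are:

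- *Likely*: "a well-known effect of the device or clearly not related to the subject or environmental factors".
- *Probably*: "is known or suspected effect of device or cannot be readily explained by subject or study procedures".
- *Possibly*: the event may be an effect of the device, or it "can be explained by the subject or study procedures".
- *Unlikely*: "is not a suspected effect of the device or can readily be explained by the subject or environmental factors".

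The fifth, *unrelated*, requires that the event is not a known device effect and is easily explained by the subject or the environment. It is the only grade whose two conditions are joined by *and*.

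Relatedness is used elsewhere:

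- **9.4.2:** "Investigators from all participating sites should report all unexpected and related adverse events, regardless of whether they are serious or not". No grade is named as the cut-off for related.
- **9.2:** a serious event after the study period is recorded and reported if it is considered possibly related to the intervention or to participation.
- **9.4:** the initial narrative report asks for association with the study intervention, a third object beside procedures and device.

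On expected harm, 11.1 says: "Risks that may be experienced from any injection are swelling bruising, redness, itching, infection, or pain".

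**The concern.** A causality scale needs one cause under assessment and a separate set of competing explanations. In 9.3 the study procedures are the cause in the opening sentence and a competing explanation in two grades. In this trial the injection is the intervention, so procedure-caused events are the ordinary case.

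At stake is whether two assessors given the same procedural event would record the same grade, and whether one of them could properly record *unlikely*. That would matter wherever a report depends on the event being called related.

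**Working it through.** No figure is involved; the check is to apply each definition literally. Two kinds of event are taken, both caused by the injection and not by the subject or the environment:

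- **Case A:** not a suspected device effect.
- **Case B:** also a well-known device effect.

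| Grade | Device condition (A / B) | Competing explanations named | Alternative-cause condition (A / B) | Joined by | Result A | Result B |
|---|---|---|---|---|---|---|
| Likely | no / yes | subject, environment | yes / yes | or | met | met |
| Probably | no / yes | subject, study procedures | no / no | or | not met | met |
| Possibly | no / yes | subject, study procedures | yes / yes | or | met | met |
| Unlikely | yes / no | subject, environment | no / no | or | met | not met |
| Unrelated | yes / no | subject, environment | no / no | and | not met | not met |

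Case A fits the first, third and fourth grades and skips the second, so the scale is not ordered for purely procedural harm. Case B fits the first three. In both cases *likely* is available; the text permits a lower grade but does not require it.

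Next, would changing every *or* to *and* be enough, with nothing else altered?

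- **Case A** then fails *likely*, *probably* and *possibly* (no device effect), and fails *unlikely* and *unrelated* (neither subject nor environment explains it). It has no grade.
- **Case B** meets *likely* and *possibly* but not *probably*, because the procedure still counts as an alternative explanation.

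So the connective alone does not repair the scale.

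Finally, apply all the changes together: the assessed cause is the injection procedure or the device, the alternatives are subject or environmental factors, and the conditions are joined by *and*. Case A is now an effect of an assessed cause with no alternative explanation. It meets *probably*, and also *likely* if it is a well-known effect of the procedure. It no longer meets *possibly* or *unlikely*. Case B meets *likely* and *probably* only.

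**The case against.** The strongest reply is that little follows in practice, and much of it stands.

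- **Grading.** A reader might infer that injection harm is necessarily graded down. It is not: *likely* remains open through its second condition, and nothing tells the assessor to take the lowest grade that fits.
- **Expected reactions.** A reader might infer that reports of the reactions in 11.1 are lost at the 9.4.2 test. They are listed risks, so they are not unexpected whatever their grade. Nor does 11.1 say that they are not device effects; it attributes the tissue loss from intravascular injection to products containing hyaluronic acid.
- **Other routes.** A reader might infer that 9.4.2 is the only path for non-serious events. The same sentence also sends unanticipated problems to the sponsor, and 9.4 covers adverse reactions, unanticipated device effects and complaints under institutional and federal policies. All adverse events are recorded (9.2), and any serious event during the study goes to the sponsor within 24 hours, with no causality condition.
- **Cut-off.** *Possibly* is a related grade by name, and 9.2 treats that level as sufficient for serious events after the study period. A move to *possibly* is not shown to lose a report.
- **Analysis.** Section 8 plans no table by relatedness.

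What the reply does not remove is the contradiction within 9.3, or the fact that *unlikely* is also open to a purely procedural event. That grade falls below the level named in 9.2 and would not normally be read as related under 9.4.2.

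**Conclusion.** The point holds as an internal inconsistency with a limited consequence. Two of five grades count the assessed cause as an alternative explanation, all five name only the device, and a purely injection-caused event fits three grades at once. It may be graded down, and the text does not settle which grade is right.

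The reach is causality grading itself, unexpected non-serious events under 9.4.2 and serious events after the study period under 9.2. No lost report has been demonstrated.

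The conclusion assumes that the definitions are applied as written, that study procedures include the injection (as section 6 indicates), and that the 9.3 grade is what decides relatedness in 9.2 and 9.4.2, which the protocol implies but does not state.

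**What to change.** Reword 9.3 as one edit:

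1. In the opening sentence and all five grades, make the assessed cause the study injection procedure or the device.
2. In *probably* and *possibly*, replace study procedures with environmental factors, as in the other three grades.
3. Join the two conditions of every grade with *and*. For *possibly*: a possible effect of the procedure or device that could also be explained by the subject or environmental factors. Making change 2 while keeping *or* would create a new overlap, since an event explained by the environment would fit both *possibly* and *unlikely*.

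Two details should be settled in the same edit so that the grades do not overlap. *Likely* would lie inside *probably*, and *unlikely* and *unrelated* would still share events, so add that the outer grade is recorded when both of a pair are met. *Unrelated* excludes only known effects, so a suspected effect with a ready alternative explanation would fit both it and *possibly*; let it exclude suspected effects too.

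The cost is a rewording of the whole of 9.3, with no change to treatment, visits or data collected. The small downside is that somewhat more events may be classed as related.

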9.4 Reporting of Adverse Events, Adverse Device Effects and Unanticipated Problems

Investigators and the protocol sponsor (which may or may not be a Penn Investigator) must conform to the adverse event reporting timelines, formats and requirements of the various entities to which they are responsible,

If the report is supplied as a narrative, the minimum necessary information to be provided at the time of the initial report includes:

- | | |
|---|--|
| 
• Study identifier• Study Center• Subject number• A description of the event• Date of onset | 
• Current status• Whether study intervention was discontinued• The reason why the event is classified as serious• Investigator assessment of the association between the event and study intervention |
|---|--|

Additionally, all other events (unanticipated problems, adverse reactions, unanticipated adverse device effects and subject complaints will be recorded and reported with respect to institutional and federal policies.

9.4.1 Follow-up report

If an SAE has not resolved at the time of the initial report and new information arises that changes the investigator's assessment of the event, a follow-up report including all relevant new or reassessed information (e.g., concomitant medication, medical history) should be submitted to the IRB. The investigator is responsible for ensuring that all SAE are followed until either resolved or stable.

9.4.2 Investigator reporting: notifying the study sponsor

Investigators from all participating sites should report all unexpected and related adverse events, regardless of whether they are serious or not, and all unanticipated problems to the sponsor.

Any study-related unanticipated problem posing risk to subjects or others, and any type of serious adverse event, will be reported to the study sponsor by telephone within 24 hours of the event. To report such events, a Serious Adverse Event (SAE) form will be completed by the investigator and emailed to the study sponsor within 24 hours. The investigator will keep a copy of this SAE form on file at the study site. Report serious adverse events by sending via email to:

CONFIDENTIAL

This material is the property of the University of Pennsylvania.

[Galderma Laboratories, L.P., email: [name] <[contact]>]

Within the following 48 hours, the investigator will provide further information on the serious adverse event or the unanticipated problem in the form of a written narrative. This should include a copy of the completed Serious Adverse Event form, and any other diagnostic information that will assist the understanding of the event. Significant new information on ongoing serious adverse events should be provided promptly to the study sponsor.

9.4.3 Investigator reporting: notifying the Penn IRB

For single and multi-site studies each site PI will need to follow their local IRB reporting requirements in addition to the protocol outlined reporting.

9.4.4 Sponsor reporting: Notifying Participating Investigators

For clinical trials, in addition to reporting certain unanticipated problems and adverse events noted above to the FDA, it is the responsibility of the study sponsor to report those same adverse events or findings to participating investigators.

9.5 Medical Monitoring

It is the responsibility of the site Principal Investigator to oversee the safety of the study at his/her site. This safety monitoring will include careful assessment and appropriate reporting of adverse events as noted above. The lead PI will monitor all AEs reported.

9.6 Confidentiality

Information about study subjects will be kept confidential and managed according to the requirements of the Health Insurance Portability and Accountability Act of 1996 (HIPAA). Those regulations require a signed subject authorization informing the subject of the following:

- What protected health information (PHI) will be collected from subjects in this study
- Who will have access to that information and why
- Who will use or disclose that information
- The rights of a research subject to revoke their authorization for use of their PHI.

In the event that a subject revokes authorization to collect or use PHI, the investigator, by regulation, retains the ability to use all information collected prior to the revocation of subject authorization. For subjects that have revoked authorization to collect or use PHI, attempts should be made to obtain permission to collect at least vital status (i.e. that the subject is alive) at the end of their scheduled study period.

9.7 Data Collection and Management

REDCap will be used to store and maintain the primary study records. The data entered into REDCap will be obtained from the study-relevant patient EMRs. Study personnel will be granted access to this project created in REDCap with each user obtaining individual access authenticated by a login system. Minimal patient identifiers will be collected and stored in the REDCap database. Patient name and date of birth will be collected in REDCap.

Source data will mainly be from the patient's EMR. When the study requires data not normally collected in the patient's EMR, the case report forms will also be the source document. Data from source documents (Appendix 15.4, case report forms (case report forms definition- Appendix 15.5), will be entered into an electronic data capturing system. All source documents should be secure in private spaces with restricted access.

During procurement of data charts will be reviewed in private spaces to ensure the confidentiality of acquired data. Data will be stored for up to 7 years after completion of the last follow-up visit of the last patient randomized. Data may be collected for up to two years following the treatment.

CONFIDENTIAL

This material is the property of the University of Pennsylvania.

9.8 Records Retention

The Principal Investigator at each site is responsible for storing regulatory documents, subject files and financial records for the period specified by law. The time period for maintaining research records is defined first by HIPAA regulations that require any HIPAA-regulated information, authorizations, waivers, etc. must be maintained for at least 6 years subsequent to the Institutional Review Board (IRB) acknowledgement of the termination of the research project and secondly by DHHS regulations (45 CFR 46.115) and FDA regulations (21 CFR 56.115) state that IRB records relating to research shall be retained for at least 3 years after completion of the research.

10 Study Monitoring, Auditing, and Inspecting

10.1 Study Monitoring Plan

This study will be closely monitored by the PI and the project manager. The PI will be participating and the data will be collected by the PI and one other study team member from the patient's EMR. The study team member will enter the data into the REDCap and the project manager will monitor the entry to verify the compliance with respect to the protocol, data collection and source documents.

10.2 Auditing and Inspecting

The investigator will permit study-related monitoring, audits, and inspections by the EC/IRB, the sponsor, government regulatory bodies, and University compliance and quality assurance groups of all study related documents (e.g. source documents, regulatory documents, data collection instruments, study data etc.). The investigator will ensure the capability for inspections of applicable study-related facilities (e.g. pharmacy, diagnostic laboratory, etc.).

Participation as an investigator in this study implies acceptance of potential inspection by government regulatory authorities and applicable University compliance and quality assurance offices.

11 Ethical Considerations

This study is to be conducted in accordance with applicable US government regulations and international standards of Good Clinical Practice, and applicable institutional research policies and procedures.

This protocol and any amendments will be submitted to a properly constituted independent Ethics Committee (EC) or Institutional Review Board (IRB), in agreement with local legal prescriptions, for formal approval of the study conduct. The decision of the EC/IRB concerning the conduct of the study will be made in writing to the investigator and a copy of this decision will be provided to the sponsor before commencement of this study.

All subjects for this study will be provided a consent form describing this study and providing sufficient information for subjects to make an informed decision about their participation in this study. This consent form will be submitted with the protocol for review and approval by the EC/IRB for the study. The formal consent of a subject, using the EC/IRB-approved consent form, must be obtained before that subject undergoes any study procedure. The consent form must be signed by the subject or legally acceptable surrogate, and the investigator-designated research professional obtaining the consent.

11.1 Risks

All treatments used in this protocol will be used according to the FDA approved intended use. No unexpected risks should occur. Risks that may be experienced from any injection are swelling bruising, redness, itching, infection, or pain.

All HA containing products have the risk of potential tissue loss if there is unrecognized intravascular injection of the fillers. All HA fillers are dissolvable and if you are strongly dissatisfied with the treatment filler or if there is evidence of tissue threat, HA can be removed with hyaluronidase (Vitrase)®. Restylane Silk carries an extra risk of hyperpigmentation to the risks from injection listed above. A risk related to all injectables used in this study is unevenness or lumps.

CONFIDENTIAL

This material is the property of the University of Pennsylvania.

Reproductive risks: If patient is of child-bearing potential, a urine pregnancy test may be administered prior to injection to confirm negative pregnancy status. The effects of this drug/device, there could be serious harm to unborn children or children who are breast-feeding. These effects could also harm the mother.

